4.2.3 Arm 2 (control arm)

ARM 2	Week 1	Week 2	Week 4	Week 6	Weeks 9 ¹ , 17 ² , 25 ² , 33 ² , 41 ² , 49 ²
History and Physical Examination	X	X	X	X	X
CBC, BMP, LFTs, Amylase, Lipase	X	X	X	X	X
Activity Data Download ³	X	X	X	X	X
QoL Assessments		X	X	X	X
Correlative Study Blood Draw		X		X	X
CT C/A/P					X
Stereotactic Radiotherapy (SBRT) ⁴	XXX				

1. +/- 1 week

2. +/- 2 weeks

3. For subjects who opt to participate in this part of the study

4. SBRT is only required for subjects with limited disease burden.

SBRT should be delivered in 1, 3, or 5 fractions per target and may continue beyond Week 1 when treating multiple sites.

Standard systemic therapy may be administered at any time for subjects with extensive disease burden and any time after completion of all planned SBRT for subjects with limited disease.

4.3 Primary Endpoints

- Phase I: Dose-limiting toxicity (DLT), as defined in Section 7.2.
- Phase II: Progression-free survival (PFS) duration, defined as time from study registration until disease progression (scored using iRECIST⁸⁴) or death, whichever comes first.

4.4 Secondary Endpoints

- Overall survival (OS) duration, defined as time from study registration until death.
- Radiographic responses, scored using iRECIST and RECIST.
- Patient-reported outcomes (PROs), assessed using the EORTC QLQ-C30 and QLQ-LC13
- Physical activity metrics, including daily step counts, obtained using wearable devices
- Correlative studies, including measures of DC expansion and DC maturation, anti-drug antibodies (ADA), and CDX-1140 pharmacokinetics

5.0 STUDY THERAPY – ARM 1

5.1 Stereotactic Body Radiotherapy

5.1.1 Patient Selection – Limited v. Extensive Disease

Stereotactic body radiotherapy (SBRT) will be administered to all subjects on Arm 1 and to subjects with limited disease burden on Arm 2. For the purposes of this trial, “limited disease” is defined as disease that, in the estimation of the treating physician, can reasonably and safely be addressed in a comprehensive fashion with SBRT. This definition will generally align with recent consensus definitions of oligometastatic disease, such as having 5 or fewer active lesions⁸⁵⁻⁸⁷. Occasionally, a

study subject with 5 or fewer active lesions may be deemed to be ineligible for comprehensive SBRT due to large target size (above **7 cm for lung tumors**⁸⁸ or above **5 cm for other lesions**^{89,90}), target location adjacent to a radiosensitive normal structure, or prior radiotherapy exposure. Rarely, comprehensive SBRT a subject with 6 or more active lesions may be deemed feasible and safe (e.g., two small lung tumors, two small liver metastases, and two spine metastases). Any subject with more than 10 active lesions will be deemed to have extensive disease⁹¹.

5.1.2 SBRT Timing

For subjects on Arm 1, SBRT will be delivered concurrently with FLT3 ligand during Week 1 of study therapy. If only one lesion is being treated, SBRT should be completed during week 1 (e.g., with daily treatments for a 5-fraction course of treatments every other day for a 3-fraction course). In cases where multiple lesions are being treated with SBRT (Arm 1 or Arm 2) or if treatment is interrupted due to technical issues or intercurrent illness, SBRT may extend beyond Week 1.

5.1.3 Immobilization, Simulation, and Localization

Patients will be positioned in a stable position capable of allowing accurate reproducibility of the target position from treatment to treatment. A variety of immobilization systems may be used, including stereotactic frames that surround the patient on three sides and large rigid pillows (conforming to patients' external contours) with reference to the stereotactic coordinate system. Patient immobilization must be reliable enough to ensure that the gross tumor volume (GTV) does not deviate beyond the confines of the planning treatment volume (PTV) with any significant probability (i.e., < 5%).

For thoracic and upper abdominal radiotherapy targets, special considerations will be made to account for the effect of internal organ motion (e.g., breathing) on target positioning and reproducibility. Acceptable maneuvers include reliable abdominal compression, accelerator beam gating with the respiratory cycle, active breath-holding techniques, and use of 4D simulation CT to generate internal target volumes (ITVs). Internal organ inhibition maneuvers must be reliable enough to ensure that the GTV does not deviate beyond the confines of the PTV with any significant probability (i.e., < 5%).

Computed tomography will be the primary image platform for targeting and treatment planning. Axial acquisitions with gantry 0 degrees and spacing ≤ 3.0 mm between scans in the region of the tumor are required. Images will be transferred to the treatment planning system for radiotherapy planning.

Verification CT scans should be obtained immediately before each treatment to ensure proper alignment of the geometric center (isocenter) of the simulated fields. Verification CT scans and/or portal films during or following each treatment may be acquired at the discretion of the treating physician.

5.1.4 Target Volumes

Parenchymal lung tumors greater than 7 cm in maximal diameter and other lesions greater than 5 cm in maximal diameter cannot serve as SBRT target lesions for this trial. Study subjects with lesions exceeding these size criteria are considered to have “Extensive” disease and will not receive SBRT to all active lesions. A smaller lesion must be chosen as the SBRT target for such patients.

Gross tumor volumes (GTVs) for target lesions will be drawn on simulation CT imaging, using appropriate window levels. Other imaging modalities (e.g., PET, MRI) imaging may be fused to simulation CT scans to aid with localization of target lesions.

Respiratory motion management for thoracic and upper abdominal tumors is required. A deep inspiration breath hold (DIBH) technique may be utilized to eliminate respiratory motion. In other cases, 4D CT simulation will be employed. If 4D CT simulation is used, GTVs should be generated on each CT phase that will be used for treatment (typically 4/10 phases if respiratory gating is employed or 10/10 phases if the patient will be treated while breathing freely). These GTVs will be combined to form internal target volumes (ITVs).

No clinical target volumes (CTVs) will be employed in this protocol.

GTVs or ITVs will be expanded to form planning target volumes (PTVs), using expansions of 4-5 mm in all directions. Expansion may be increased by up to 5 additional mm in the craniocaudal directions if there is concern for unmeasured respiratory motion (e.g., in cases of limited 4D CT quality for thoracic or upper abdominal targets).

5.1.5 SBRT Dosing

SBRT doses for this study follow NCCN guidelines⁷⁵ and cooperative group recommendations³³.

Lung tumors:

Schedule	Criteria
34 Gy x 1	Peripheral tumor measuring ≤ 2 cm in greatest dimension and > 1 cm from the chest wall
18 Gy x 3	Peripheral tumor measuring ≤ 5 cm and not eligible for 34 Gy x 1 fraction
10 Gy x 5	Central or peripheral tumor not eligible for 34 Gy x 1 fraction or 18 Gy x 3 fractions

A “central” lung tumor will be defined based on the eligibility criteria for RTOG 0813³⁴ (“Seamless Phase I/II Study of Stereotactic Lung Radiotherapy (SBRT) for Early Stage, Centrally Located, Non-Small Cell Lung Cancer (NSCLC) in Medically Inoperable Patients”): Tumor within or touching the zone of the proximal bronchial tree, defined as a volume 2 cm in all directions around the proximal bronchial tree (carina, right and left main bronchi, right and left upper lobe bronchi, intermedius bronchus, right middle lobe bronchus, lingular bronchus right and left lower lobe bronchi). [See figure below] Tumors that are immediately adjacent to mediastinal or pericardial pleura (PTV touching the pleura) also are considered central tumors. Tumors that are not “central” are considered to be “peripheral.”

Other target lesions:

Schedule	Target Lesion Location
10 Gy x 3	Spinal or Paraspinal
10 Gy x 3	Osseous
10 Gy x 5	Mediastinal or Cervical Lymph Node
15 Gy x 3	Liver
15 Gy x 3	Abdominal or Pelvic (lymph node or adrenal gland)

5.1.6 Target Coverage

At least 95% of each PTV should receive the full prescription dose. If this cannot be achieved while respecting normal tissue constraints, the prescription dose may be lowered by up to 30%. Alternatively, the portion of the PTV abutting/overlapping a radiosensitive structure may be excluded from the target coverage evaluation structure ("PTV_eval").

5.1.7 Critical Structures

Normal tissue structures visualized on the simulation CT will be delineated using contouring guidelines established by RTOG:

<https://www.rtog.org/CoreLab/ContouringAtlases.aspx>

The following normal tissue constraints, adopted from 2020 NCCN guidelines⁷⁵ and RTOG 0813³⁴, will be used for planning SBRT to lung tumors:

	1 Fraction	3 Fractions	5 Fractions
Brachial plexus	max dose < 17.5 Gy	max dose < 24 Gy	max dose < 32 Gy
Esophagus	max dose < 15.4 Gy	max dose < 30 Gy	max dose < 52.5 Gy
Great vessels	max dose < 37 Gy	max dose < 39 Gy	max dose < 52.5 Gy
Heart/pericardium	max dose < 22 Gy	max dose < 30 Gy	max dose < 52.5 Gy
Lungs	At least 1500 cc receiving < 12.5 Gy	At least 1500 cc receiving < 12.5 Gy	At least 1500 cc receiving < 12.5 Gy
Skin	max dose < 26 Gy	max dose < 24 Gy	max dose < 32 Gy
Spinal cord	max dose < 14 Gy	max dose < 18 Gy	max dose < 30 Gy
Stomach	max dose < 12.4 Gy	max dose < 27 Gy	max dose < 35 Gy
Trachea and proximal bronchi	max dose < 20.2 Gy	max dose < 30 Gy	max dose < 52.5 Gy

The following normal tissue constraints, adopted from NRG-BR001^{33,92}, will be used for planning SBRT to other target lesions:

OAR Dose Limits for 3 fraction SBRT			
Serial Organ	Volume	Volume Dose (Gy)	Avoidance Endpoint (Reference)
Spinal Cord	<0.03 cc	22.5	Myelitis (Timmerman)
	<1.2 cc	13	Myelitis (Timmerman)
Ipsilateral Brachial Plexus	< 0.03 cc	26	Brachial Plexopathy (Timmerman)
	<3 cc	22	Brachial Plexopathy (Timmerman)
Cauda Equina	<0.03 cc	25.5	Neuritis (Timmerman)
	<5 cc	21.9	Neuritis (AAPM TG-101)
Sacral Plexus	<0.03 cc	24	Neuropathy (AAPM TG-101)
	<5 cc	22.5	Neuropathy (AAPM TG-101)
Trachea and Ipsilateral Bronchus*	<0.03 cc	30	Stenosis/Fistula (Z4099)
	<5cc	25.8	Stenosis/Fistula (Timmerman)
Esophagus*	<0.03 cc	27	Stenosis/Fistula (Timmerman 2006 /RTOG 0618)
	<5cc	17.7	Stenosis/Fistula (Z4099)
Heart/Pericardium	<0.03cc	30	Pericarditis (Z4099)
	<15 cc	24	Pericarditis (Z4099)
Great vessels*	<0.03cc	45	Aneurysm (Z4099)
	<10 cc	39	Aneurysm (Z4099)
Skin	<0.03cc	33	Ulceration (Z4099)
	<10cc	31	Ulceration (Timmerman)
Stomach	<0.03cc	30	Ulceration/Fistula (Timmerman)
	<10cc	22.5	Ulceration/Fistula (Timmerman)
Duodenum*	<0.03cc	24	Ulceration (Timmerman 2006)
	<10cc	15	Ulceration (Timmerman 2006)
Bowel*	<0.03 cc	34.5	Ulceration (Timmerman)
	<20cc	24	Colitis/Fistula (Z4099)
Rectum*	<0.03 cc	49.5	Ulceration (Timmerman)
	<3.5 cc	45	Proctitis/Fistula (Timmerman)
Bladder	<0.03cc	27.5	Proctitis/Fistula (Timmerman)
	<15 cc	16.8	Cystitis/Fistula (AAPM TG-101)
Ureter	<0.03 cc	40	Stenosis (Timmerman)
Penile bulb	< 3cc	25	Impotence (Timmerman)
Femoral heads	<10 cc	24	Necrosis (Timmerman)
Bile duct	< 0.03 cc	36	Stenosis (Timmerman)
Renal hilum/vascular trunk	<15 cc	19.5	Malignant Hypertension (Timmerman)
Rib	< 0.03 cc	50	Pain or Fracture (Timmerman)
	<5 cc	40	Pain or Fracture (Timmerman)
Parallel Organ	Volume	Volume Dose (Gy)	Avoidance Endpoint (Reference)
Lung (total)	<15% lung volume	20	Pneumonitis/Lung Function (RTOG 0618)
	< 37% lung volume	11	Pneumonitis (Timmerman)
	1500 cc	10.5	Basic Lung Function (Z4099)
	1000 cc	11.4	Pneumonitis (Z4099)
Ipsilateral kidney	<130 cc	12.3	Nephritis (Timmerman 2006)
Total Kidney	<200cc	15	Basic Renal Function (Timmerman)
Liver	<700 cc	17.1	Liver function (Timmerman 2006/Z4099)

*NOTE: Avoid circumferential irradiation.

OAR Dose Limits for 5 fraction SBRT			
Serial Organ	Volume	Volume Dose (Gy)	Avoidance Endpoint
Spinal Cord	<0.03 cc	28	Myelitis (Timmerman)
	<0.35 cc	22	Myelitis (Timmerman)
Ipsilateral Brachial Plexus	<1.2 cc	15.6	Myelitis (Timmerman)
	<3 cc	32	Brachial Plexopathy (RTOG 0813)
Cauda Equina	<0.03 cc	30	Brachial Plexopathy (RTOG 0813)
	<5 cc	32	Neuritis (AAPM TG-101)
Sacral Plexus	<0.03 cc	30	Neuritis (AAPM TG-101)
	<5 cc	30	Neuropathy (AAPM TG-101)
Trachea and Ipsilateral Bronchus*	<0.03cc	40	Stenosis/Fistula (Timmerman)
	<5cc	32	Stenosis/Fistula (RTOG 0813)
Esophagus*	<0.03cc	35	Stenosis/Fistula (Timmerman)
	<5 cc	27.5	Stenosis/Fistula (RTOG 0813)
Heart/Pericardium	<0.03 cc	38	Pericarditis (Timmerman)
	<15 cc	32	Pericarditis (RTOG 0813)
Great vessels*	<0.03 cc	53	Aneurysm (Timmerman)
	<10 cc	47	Aneurysm (RTOG 0813)
Skin	< 0.03cc	38.5	Ulceration (Timmerman)
	< 10cc	36.5	Ulceration (Timmerman)
Stomach	< 0.5cc	35	Ulceration/Fistula (Timmerman)
	< 5cc	26.5	Ulceration/Fistula (Timmerman)
Duodenum*	< 0.5 cc	30	Ulceration (RTOG 1112)
	< 5 cc	18.3	Ulceration (Timmerman 2006)
Bowel*	< 0.03 cc	40	Ulceration (Timmerman)
	< 20 cc	28.5	Colitis/Fistula (Timmerman)
Rectum*	<0.03 cc	55	Ulceration (Timmerman)
	<3.5 cc	50	Proctitis/Fistula (Timmerman)
Bladder	< 0.03 cc	32.5	Proctitis/Fistula (Timmerman)
	< 15 cc	38	Cystitis/Fistula (Timmerman)
Ureter	< 0.03 cc	20	Cystitis/Fistula (Timmerman)
	< 0.03 cc	45	Stenosis (Timmerman)
Penile Bulb	<3 cc	30	Impotence (Timmerman)
Femoral head	<10 cc	30	Necrosis (Timmerman)
Bile Duct	<0.03 cc	41	Stenosis (Timmerman)
Renal hilum/Vascular Trunk	<15 cc	23	Malignant Hypertension (Timmerman)
Rib	<0.03 cc	57	Pain or Fracture (Timmerman)
	<5 cc	45	Pain or Fracture (Timmerman)
Parallel Organ	Volume	Volume Dose (Gy)	Avoidance Endpoint
Lung (total)	<37% lung volume	13.5	Pneumonitis (Timmerman)
	< 1500 cc	12.5	Basic Lung Function (RTOG 0813)
	< 1000 cc	13.5	Pneumonitis (RTOG 0813)
	< 130 cc	14.5	Basic Renal Function (Timmerman)
Total Kidney	<200cc	18	Basic Renal Function (Timmerman)
Liver	<700 cc	21	Liver Function (Timmerman)

*NOTE: Avoid circumferential irradiation.

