4 patients who received CDX-1140 monotherapy experienced severe treatment-related pneumonitis, with 3 of the 4 developing pneumonitis during the first week of treatment. These patients developed shortness of breath, and imaging of the lungs demonstrated new inflammatory changes. Two patients required intubation. All four patients were treated with high dose corticosteroids, and two of the patients subsequently died, due to a documented infection in one patient and presumed infection in the other. Two patients demonstrated clinical improvement temporally associated with the administration of tocilizumab. Of note, tocilizumab has not been incorporated into the treatment guidelines for management of pneumonitis associated with immune checkpoint blockade therapy,¹⁰² but there is a case series suggesting that tocilizumab is effective in the management of corticosteroid-refractory pneumonitis irAEs¹⁰³. Based on the rapid response temporally associated with the administration of tocilizumab in the cases discussed above, and the case series suggesting that tocilizumab may be beneficial in treating checkpoint-related pneumonitis, tocilizumab should be considered as a therapeutic option in those patients with CDX-1140 related, steroid-refractory pneumonitis, as well as for other high grade steroid-refractory adverse events.

Thrombosis

CD40 is functionally expressed on platelets and endothelial cells, and CD40 signaling could theoretically promote a pro-thrombotic state. In the CDX1140-01 study, 1 patient developed a deep vein thrombosis and pulmonary embolism that was considered related to CDX-1140. Administration of CP-870,893, another agonist anti-CD40 mAb, was associated with transient increases in D-dimer and thrombin-antithrombin 3 complex formation levels at the 2 highest doses tested (0.2 and 0.3 mg/kg) in the Phase 1 study⁶³. Standard coagulation parameters were not affected by CP-870,893. One patient with a prior history of deep vein thrombosis had a drug-related thromboembolic dose-limiting toxicity.

Elevated liver enzymes

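### The lung-tumor constraint table repeats a 12.5 Gy lung limit at 1, 3 and 5 fractions; at 3 fractions this is about 1.3-fold looser in BED than the protocol's own 10.5 Gy and is probably a 5-fraction value carried across columns

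*Combined protocol and SAP*

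**What the plan says.** Section 5.1.7 holds two sets of normal-tissue limits, separated by target.

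- **Lung tumors** (sources named as 2020 NCCN guidelines and RTOG 0813). The lung row reads "At least 1500 cc receiving < 12.5 Gy" in all three fraction columns. The other eight organs each have a different limit in every column.
- **Other lesions** (source named as NRG-BR001). These limits "will be used for planning SBRT to other target lesions". The 3-fraction table sets 10.5 Gy at 1500 cc, labelled "Basic Lung Function (Z4099". The 5-fraction table sets 12.5 Gy at 1500 cc, labelled "Basic Lung Function (RTOG 0813".

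Section 5.1.5 gives 18 Gy x 3 to a "Peripheral tumor measuring ≤ 5 cm and not eligible for 34 Gy x 1 fraction". It also treats liver, spinal, osseous and abdominal or pelvic lesions in 3 fractions. Section 5.1.6 provides that, if coverage cannot be met within the constraints, "the prescription dose may be lowered by up to 30" percent.

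**The concern.** A fixed total dose does more biological damage when given in fewer fractions, so a limit on total dose would normally fall as the number of fractions falls. The two sets of limits agree on the lungs at 5 fractions and part at 3. There the lung-tumor table keeps the figure that the protocol elsewhere ties to 5 fractions.

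For 18 Gy x 3 lung plans this row is the only numeric lung limit. The further 3-fraction lung limits (15% and 37% of lung volume, and 1000 cc) appear only in the other-lesion table. A subject whose lung tumor is treated in 3 fractions therefore has a weaker safeguard for lung function than one whose liver or spine lesion is treated in 3 fractions. Both can be the same subject: the example of comprehensive SBRT in Section 5.1.1 is "two small lung tumors, two small liver metastases, and two spine metastases".

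**Working it through.** **Inputs.** Total-dose limits D and fraction numbers n come from Section 5.1.7. The documents give no alpha/beta; 3 Gy is assumed, with 5 and 2 Gy as the range. The 1500 cc rows are read as volume to be spared. The lung-tumor table names no endpoint; basic lung function is inferred from the matching 1500 cc / 12.5 Gy row in the 5-fraction table.

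**Formula.** BED = D × (1 + (D/n)/(alpha/beta)).

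**Lung limits at alpha/beta 3**

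- 12.5 Gy in 5: 12.5 × (1 + 2.5/3) = 22.92 Gy
- 10.5 Gy in 3: 10.5 × (1 + 3.5/3) = 22.75 Gy
- 12.5 Gy in 3: 12.5 × (1 + 4.167/3) = 29.86 Gy

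| alpha/beta | 12.5 in 5 | 10.5 in 3 | 12.5 in 3 | 12.5 in 3 v 10.5 in 3 | 12.5 in 3 v 12.5 in 5 |
|---|---|---|---|---|---|
| 2 | 28.12 | 28.88 | 38.54 | 1.34 | 1.37 |
| 3 | 22.92 | 22.75 | 29.86 | 1.31 | 1.30 |
| 5 | 18.75 | 17.85 | 22.92 | 1.28 | 1.22 |

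In raw dose, 12.5/10.5 = 1.19. That 12.5 Gy in 3 exceeds 12.5 Gy in 5 holds at any alpha/beta; only the size depends on the assumption.

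**What 3-fraction dose matches 12.5 Gy in 5?** Solving D + D²/(3 × alpha/beta) = BED of 12.5 Gy in 5 gives 10.55 Gy at alpha/beta 3, and 10.3 Gy at 2. The protocol's own 10.5 Gy is almost exactly this figure.

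**Do the protocol's other paired lung limits behave this way?** In the other-lesion tables at alpha/beta 3, the 1000 cc pair (11.4 Gy in 3, 13.5 Gy in 5) gives 25.8 v 25.7 Gy. The 37% pair (11 Gy in 3, 13.5 Gy in 5) gives 24.4 v 25.7 Gy. With the 1500 cc pair, all three agree within about 5%.

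**Is lung unusual within its own table?** Ratio of 3-fraction to 5-fraction BED, alpha/beta 3:

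| Row | Limits, 3 v 5 fractions (Gy) | Ratio |
|---|---|---|
| Esophagus | 30 v 52.5 | 0.55 |
| Heart | 30 v 52.5 | 0.55 |
| Trachea/bronchi | 30 v 52.5 | 0.55 |
| Spinal cord | 18 v 30 | 0.60 |
| Brachial plexus | 24 v 32 | 0.88 |
| Skin | 24 v 32 | 0.88 |
| Great vessels | 39 v 52.5 | 0.88 |
| Stomach | 27 v 35 | 0.93 |
| **Lung** | **12.5 v 12.5** | **1.30** |

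Eight rows lie between 0.55 and 0.93. Lung alone is above 1.

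**The case against.** The strongest reply is that Section 5.1.7 assigns each set of limits by target and names a source for each, so every plan has one governing table. That stands. A reader might infer that the protocol contradicts itself, or leaves open which table governs a plan; the text does not support either. What it leaves unstated is narrower: whether the stricter 3-fraction lung figure should hold for the lungs as a whole when one subject has both kinds of target.

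The two sets also differ widely elsewhere. At 3 fractions, seven of nine shared rows differ: five are tighter in the lung-tumor table and two looser (lung, and esophagus at 30 v 27 Gy). At 5 fractions the gaps are larger, for example esophagus 52.5 v 35 Gy, which is 2.03-fold in BED. So disagreement between tables is weak evidence of a mistake. The better evidence is the comparison of lung's 3- and 5-fraction cells within its own table, together with the near-equality of 10.5 Gy in 3 and 12.5 Gy in 5.

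Nor is the lung-tumor table isoeffective across all columns. At alpha/beta 3 the 1-fraction limit exceeds the 3-fraction limit in BED in six of the eight other rows (skin 2.86-fold, great vessels 2.37-fold). This stands too, and it is why nothing here rests on the 1-fraction column.

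Finally, the named source may itself print 12.5 Gy for every schedule. That cannot be checked from the documents. If it does, the table is a faithful copy, but the 3-fraction figure would still be looser than the one the protocol adopts for other lesions.

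**Conclusion.** The concern holds as a minor planning-safety point. The 3-fraction lung limit for lung tumors is about 1.3-fold looser in BED than the protocol's 10.5 Gy in 3 (1.28 to 1.34) and than its 12.5 Gy in 5 (1.22 to 1.37), for alpha/beta 5 to 2. Probably a 5-fraction value was carried across columns; that is an inference, not something the documents prove.

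A reader might go further and link this limit to the deaths after CDX-1140 pneumonitis, or to the DLT count. The documents do not support that. The row's inferred endpoint is preserved lung function, and Section 5.2.6 reports the two deaths as "due to a documented infection in one patient and presumed infection in the other". Any effect on DLTs would be indirect.

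The limit will rarely bind, mainly with several lung targets or small lungs. Section 5.1.1 presents its six-lesion example as rare, and small lung tumors may qualify for 34 Gy x 1 and so avoid the 3-fraction schedule. SBRT is delivered by the same rules on both arms, so the PFS comparison is not biased, and no sample size, power or error rate changes.

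**What to change.** In the lung-tumor table of Section 5.1.7:

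1. Set the 3-fraction lung cell to at least 1500 cc below 10.5 Gy, the protocol's own 3-fraction value. Leave 12.5 Gy in the 5-fraction column.
2. Add a sentence applying that same limit to the lungs when lung and other lesions are both treated in 3 fractions.
3. Have the radiation oncology team check the 1-fraction cell against a single-fraction source. The documents give no figure for it, so none is proposed.

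The cost is an amendment with one cell changed, one checked and one sentence added; no procedures are added. An occasional subject with several lung targets or small lungs may need the dose reduction that Section 5.1.6 already allows, with possible loss of local control in that lesion.

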5.2 CDX-301 and CDX-1140

5.2.1 Dosing and Administration

CDX-301

Each 2 mL clear borosilicate glass vial contains 2.5 mg/mL CDX-301 glycoprotein in a 1.0 mL (with an overfill to 1.2 mL) volume of buffered solution composed of 10 mM sodium phosphate, 140 mM NaCl, pH 7.0. CDX-301 Drug Product is formulated as a sterile solution intended for single-use subcutaneous administration.

An initial study drug shipment will be provided following receipt of all required documents. Additional supplies should be ordered with at least one week advance notice using a form supplied by Celldex.

All study supplies must be stored in a secured area with limited, approved access. CDX-301 temperature must be maintained between 2° to 8°C (36 to 46°F) and monitored daily. Deviations in storage conditions must be reported to [contact] within 24 hours of awareness.

The individual dose is calculated using the actual baseline body weight of the subject according to the calculations below. All subjects will receive 75 µg/kg of CDX-301 at each administration.

$$\begin{aligned} \text{Body Weight (kg)} \times \text{Dose Level (75}\mu\text{g/kg)} &= \text{Desired Dose (\mu g)} \\ \text{Desired Dose (\mu g)} \div 2500 \mu\text{g/mL} &= \text{Volume of CDX-301 (mL)} \end{aligned}$$

For example, for an 80 kg subject, the total dose required to deliver the 75 µg/kg dose would be 6000 µg. The calculated volume required from the 2500 µg/ml CDX-301 stock solution to obtain 6000 µg of CDX-301 would be 2.4 ml. Three vials would be needed to administer this dose.

CDX-301 liquid should be withdrawn from the vial gently, avoiding foaming and excess shearing. As the maximum volume of any individual injection will be 2.0 ml, the dose may be split into up to 3 separate syringes/subcutaneous injections as needed to administer the required volume.

CDX-301 will be administered as a daily subcutaneous injection. The injection site may be rotated between the extremities. CDX-301 injections should not be given to areas of skin with conditions such as scarring, tattoos or persistent injection site reactions that will not allow easy access for study drug administration or evaluation of localized adverse events. CDX-301 administration will be performed within the clinical setting by trained staff personnel.

CDX-1140

Each vial to be used for intravenous administration contains a nominal 3.0 mg/mL CDX-1140 protein in a 10.0 mL volume of buffered solution composed of sodium phosphate, potassium phosphate, potassium chloride, sodium chloride, and polysorbate 80, with a pH of 7.0.

CDX-1140 must be stored at $\leq -65^{\circ}\text{C}$ (-85°F) until use. CDX-1140 should be protected from light. However, sufficient light protection is provided by the secondary

container (carton); no specific light protection is needed during preparation of the dosing solution and infusion.

Upon removal from storage at $\leq -65^{\circ}\text{C}$, vials should be thawed at ambient temperature for approximately 1.5 hours. After equilibration to room temperature and before use, the vial should be gently swirled to ensure uniform mixing of the contents. Do not invert or shake vials. Solution should be gently withdrawn (avoiding foaming and excess shearing).

CDX-1140 should be administered as a 90-minute infusion using a volumetric pump with a 0.22 micron pore size, low-protein binding polyethersulfone (PES) membrane in-line filter.

The CDX-1140 dose will be calculated using the actual baseline body weight of the patient. The following formula should be used to calculate the volume of CDX-1140 required for each administration:

$$\text{Body Weight (kg)} \times \text{Desired Dose (mg/kg)} \div 3 \text{ mg/mL} = \text{Volume of CDX-1140 (mL)}$$

For example, for an 80 kg subject, the total dose required to deliver the 1.5 mg/kg dose would be 120 mg. the calculated volume required from the 3 mg/mL CDX-1140 stock solution to obtain 120 mg would be 40 mL. As each vial of CDX-1140 contains a withdrawable volume of 10 mL, administration of the 1.5 mg/kg dose would require 4 vials of CDX-1140.

